CRF	case report form
CRO	contract research organization
CS	clinically significant
СТ	computerized tomography
ECG	electrocardiogram
eCRF	electronic case report form
eGFR	estimated glomerular filtration rate
ET	early termination
GCP	good clinical practice
HBsAg	Positive test results for hepatitis B surface antigen
HCV	Positive test results for hepatitis C
HERC	hepatic events review committee
HIF-PH	hypoxia-inducible factor prolyl hydroxylase
HIV	human immunodeficiency virus
HgbA1c	glycosylated hemoglobin

Abbreviation	Definition
htLV	height-adjusted liver volume
htTKV	height-adjusted total kidney volume
ICF	informed consent form
IEC	independent ethics committee
IDMC	independent data monitoring committee
IRB	institutional review board
IRT	interactive response technology
ITT	intent-to-treat
IUD	intrauterine device
IUS	intrauterine hormone-releasing system
KDIGO	Kidney Disease Improving Global Outcomes
LOE	lack of efficacy
LTSS	lixivaptan treated safety set
LV	liver volume
MAR	missing at random
МСМС	Monte Carlo Markov Chain
MedDRA	Medical Dictionary for Regulatory Activities
MI	multiple imputation
mITT	modified intent-to-treat

Abbreviation	Definition
MMRM	mixed model for repeated measurements
MNAR	missing not at random
MRI	magnetic resource imaging
NCS	non-clinically significant
P2EAS	part 2 efficacy analysis set
P2SS	part 2 safety set
PCS	potentially clinically significant
PEAS	primary efficacy analysis set
РК	pharmacokinetics
PPAS	per-protocol efficacy analysis set
PRO	patient reported outcomes
QTcF	QT interval corrected for heart rate according to Fridericia's formula
SAE	serious adverse event
SAP	statistical analysis plan
SEAS	secondary efficacy analysis set
SD	standard deviation
SDAC	Statistical Data Analysis Center
SGLT2	sodium-glucose cotransporter 2
SOC	system organ class

Abbreviation	Definition
TEAE	treatment-emergent adverse event
TEAESI	treatment-emergent adverse event of special interest
TKV	total kidney volume
ULN	upper limit of normal
WHODD	World Health Organization Drug Dictionary

Table of Contents

Approv	Approvals2				
List of	List of Abbreviations				
Table of	Fable of Contents 8				
List of	ist of Tables				
List of	ist of Figures				
1.	Introduction	14			
2.	Study Objectives1	4			
2.1	Study Objectives of the Double-blind Phase (Part 1/Year 1)1	4			
2.1	1. Primary Objective	4			
2.1	2. Key Safety Objective1	4			
2.1	3. Secondary Efficacy Objectives	4			
2.1	4. Secondary Safety Objective	4			
2.1	5. Health Outcomes Related Objectives	4			

2.1. Study Objectives of the Double-blind Phase (Part 1/Year 1)

2.1.1. Primary Objective

To demonstrate the efficacy of lixivaptan compared to placebo in the slowing of deterioration in kidney function in participants with ADPKD as demonstrated by the annualized change from baseline in estimated glomerular filtration rate (eGFR) determined from the Chronic Kidney Disease Epidemiology Collaboration (CKD-EPI) creatinine equation without the race term (CKD-EPIcr R).

2.1.2. Key Safety Objective

To compare the incidences of liver chemistry test elevations in participants randomized to lixivaptan with participants randomized to placebo.

2.1.3. Secondary Efficacy Objectives

- To compare the rate of change (slope) in on-treatment eGFR in participants treated with lixivaptan to participants treated with placebo;
- To assess the effect of lixivaptan on height-adjusted total kidney volume (TKV) as measured by magnetic resonance imaging (MRI) compared to placebo.

2.1.4. Secondary Safety Objective

To assess the non-hepatic safety and tolerability of lixivaptan.

2.1.5. Health Outcomes Related Objectives

• To evaluate medical resource utilization (e.g., medication use/changes; unplanned office visit; urgent care and emergency department usage; and hospitalizations) resulting from clinical events in participants randomized to lixivaptan compared with those on placebo

and assess which events are driving any observed differences in medical resource utilization between lixivaptan and placebo;

• To evaluate the change from baseline in domain scores of the ADPKD Impact Scale (ADPKD-IS), ADPKD Pain and Discomfort Scale (ADPKD-PDS), and ADPKD Urinary Impact Scale (ADPKD-UIS) in participants treated with lixivaptan compared with participants treated with placebo.

2.1.6. Pharmacokinetics Objective

To characterize the PK profile of lixivaptan utilizing PopPK based on sparse plasma sampling.

2.1.7. Exploratory Objectives

- To assess the effect of lixivaptan on height-adjusted liver volume (htLV) as measured by MRI compared to placebo;
- To evaluate the change from baseline in urine osmolality in participants treated with lixivaptan compared with participants treated with placebo;
- To evaluate the effect of lixivaptan on kidney function as assessed by eGFR using a novel serum creatinine and serum cystatin C-based CKD-EPI equation refit without the race variable (CKD-EPIcr-cys_R) compared with placebo.

2.2. Study Objectives of the Open-label Phase (Part 2/Year 2)

2.2.1. Key Objective

To demonstrate the continued efficacy of lixivaptan in the slowing of deterioration in kidney function in participants randomized to lixivaptan in the double-blind phase (Part 1) as measured by the annualized change from baseline (Part 2) in eGFR as determined by the CKD-EPIcr_R equation at the end of the open-label phase (Part 2).

2.2.2. Key Safety Objective

To assess the incidence of liver chemistry test abnormalities during the open-label phase.

2.2.3. Secondary Objectives

- To assess the rate of change (slope) in on-treatment eGFR in Part 2 in participants treated with lixivaptan in Part 1 and Part 2;
- To assess the effect of lixivaptan on height-adjusted TKV (htTKV) as measured by MRI in Part 2 in participants treated with lixivaptan in Part 1 and Part 2.

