8.3 Populations for Analysis

Part 1:

The following populations will be used for analyzing the data from Part 1:

Treated Safety Set: The Treated Safety Set consists of all participants who received at least 1 dose of study drug in Part 1.

Randomized Safety Set: The Randomized Safety Set consists of all participants in the Treated Safety Set who are randomized and receive at least 1 dose of randomized study drug.

Primary Efficacy Analysis Set (PEAS): The PEAS consists of all participants in the Randomized Safety Set who have both baseline and at least 1 valid assessment of eGFR in the Follow-up Period.

Secondary Efficacy Analysis Set (SEAS): The SEAS consists of all participants in the Randomized Safety Set who have both baseline and at least 1 on-treatment assessment of eGFR.

Part 2:

The following populations will be used for analyzing the data from Part 2:

Long-term Safety Set: The Long-term Safety Set consists of all participants in the Randomized Safety Set of Part 1 who receive at least 1 dose of lixivaptan during Part 2.

Long-term Full Analysis Set: The Long-term Full Analysis Set consists of all participants in the Long-term Safety Set who have at least 1 on-treatment measurement of eGFR in Part 2.

Long-term Efficacy Analysis Set: The Long-term Efficacy Analysis Set consists of all participants in the Long-term Full Analysis Set who were randomized to lixivaptan in Part 1.

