4.2.2. Other Endpoints

4.2.2.1. Other Comparison Endpoints

The additional secondary endpoints are:

- The annualized rate of change (slope) in eGFR, estimated from all on-treatment eGFRs, calculated from the CKD-EPI equation (2021 CKD-EPIcr_R) for serum creatinine during the Maintenance Treatment Period in Part 2. An on-treatment eGFR is defined as any eGFR obtained while participants are on treatment (taking lixivaptan) in Part 2.
- The annualized percent change in htTKV from baseline (post-treatment follow-up after Week 52 in Part 1) to post-treatment follow-up during Follow-up Period II after Week 104 for on-treatment completers, or, for participants who discontinue study drug treatment prior to Week 104 [Visit 42], during the Follow-up Period 28 days following study drug treatment discontinuation in Part 2.

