4.2.3.1. Exploratory Endpoints

- The annualized percent change in htLV determined by MRI from baseline (posttreatment follow-up visit [Visit 25] after Week 52 in Part 1) to post-treatment follow-up during Follow-up Period II after Week 104 for on-treatment completers, or, for participants who discontinue study drug treatment prior to Week 104 [Visit 42], during the Follow-up Period 28 days following study drug treatment discontinuation in Part 2;
- Mean change from baseline in morning spot urine osmolality in Part 2; Baseline is defined as urine osmolality obtained at 28 days post-treatment follow-up visit (Visit 25) after Week 52 in Part 1.
- The annualized change in eGFR calculated from the 2021 CKD-EPIcr-cys_R equation from baseline to the post-treatment follow-up. The definitions of baseline eGFR, post-treatment follow-up eGFR and annualization are the same as the key comparison endpoint in Part 2 (Section 4.2.1.1) except for using the different eGFR equations.

5. Analysis Populations

The following analysis populations are planned for this study:

Part 1:

- **Placebo Run-in Safety Set:** The Placebo Run-in Safety Set includes all participants who received at least one dose of placebo during Placebo Run-In Period in Part 1.
- Lixivaptan Titration Safety Set: The Lixivaptan Titration Safety Set includes all participants who received at least one dose of lixivaptan during Lixivaptan Titration Period in Part 1.
- **Randomized Safety Set:** The Randomized Safety Set includes all participants who received at least one dose of study drug after randomization.
- Intent-to-Treat Analysis Set (ITT): The ITT includes all participants who were randomized in Part 1.

- **Modified Intent-to-Treat Analysis Set (mITT):** The mITT includes all participants in the ITT who received at least one dose of study drug in Part 1. Note that the mITT Analysis Set consists of the same set of the participants in the Randomized Safety Set.
- **Primary Efficacy Analysis Set (PEAS):** The PEAS includes all participants in the mITT Analysis Set who have both baseline and at least one assessment of eGFR after the treatment is complete or discontinued in Part 1.
- Secondary Efficacy Analysis Set (SEAS): The SEAS includes all participants in the mITT Analysis Set who have both baseline and at least one on-treatment assessment of eGFR.

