- **Per-protocol Efficacy Analysis Set (PPAS):** The PPAS includes all participants in the PEAS who do not have any protocol deviations that are deemed to potentially impact efficacy.

Assignment of participants to populations will be confirmed at a blinded data review meeting to be held before the study database is locked for Part 1.

Part 2:

- **Part 2 Safety Set (P2SS):** The Part 2 Safety Set includes all participants who receive at least one dose of lixivaptan in Part 2.
- **Part 2 Efficacy Analysis Set (P2EAS):** The Part 2 Efficacy Analysis Set includes all participants in the Part 2 Safety Set who have at least one assessment of off-treatment eGFR in Part 2.

Parts 1 & 2 (Combined):

• Lixivaptan Treated Safety Set (LTSS): The Lixivaptan Treated Safety Set is defined as all participants who received at least one dose of lixivaptan treatment after randomization during the entire study. This analysis population will be used to summarize safety data during the study for all randomized, lixivaptan-treated participants.

6. General Issues for Statistical Analysis

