8.9. Other Comparison Analyses (Part 2)

8.9.1. Annualized Rate of Change (Slope) in eGFR

All the eGFR assessments for this analysis are calculated from the 2021 CKD-EPI equation (2021 CKD-EPIcr_R).

All the observed changes from baseline (mean of the 3 eGFR values obtained at off-treatment visits after Week 52 in Part 1) to all visits with on-treatment eGFR values during the Maintenance Treatment Period visits, i.e., Visit 30 (Week 56) up to Visit 42 (Week 104), while on study drug treatment in the P2EAS will be utilized for determining the annualized rate of change (slope) in eGFR. Any eGFR values obtained after 1 or more days off of study drug treatment during the Maintenance Treatment Period are excluded from the analysis.

To determine the annualized rate of change (slope) in eGFR, the average of observed changes from baseline at each visit by treatment cohort and overall will be calculated. The annualized rate of change (slope) in the eGFR will be calculated by:

The annualized rate of change (slope) in eGFR = (-6 x mean change at Visit 30 -5 x mean change at Visit 31 -4 x mean change at Visit 32 -3 x mean change at Visit 33 -2 x mean change at Visit 34 -1 x mean change at Visit 35 -0 x mean change at Visit 36 +1 x mean change at Visit 37 +2 x mean change at Visit 38 +3 x mean change at Visit 39 + 4 x mean change at Visit 40 + 5 x mean change at Visit 41 + 6 x mean change at Visit 42)/14.

The annualized rate of change (slope) from baseline in eGFR in Part 2 will be presented by treatment cohort and overall for participants in the P2EAS along with the annualized rate of change (slope) from baseline at Part 1 for the participants in each treatment cohort.

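### The Part 2 on-treatment eGFR slope is computed in a set that requires an off-treatment eGFR, and from raw visit means in place of the protocol's MMRM, so it is selected on retention

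*SAP*

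**What the plan says.** **Objective and endpoint.** The objective in SAP 2.2.3 is "To assess the rate of change (slope) in on-treatment eGFR in Part 2 in participants treated with lixivaptan in Part 1 and Part 2". SAP 4.2.2.1 builds the Part 2 slope from on-treatment values alone: "An on-treatment eGFR is defined as any eGFR obtained while participants are on treatment (taking lixivaptan) in Part 2". Neither place requires an off-treatment value.

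**Analysis set.** SAP 8.9.1 takes changes at Visits 30 to 42 "while on study drug treatment in the P2EAS will be utilized for determining the annualized rate of change (slope) in eGFR". SAP 5 says that the P2EAS "includes all participants in the Part 2 Safety Set who have at least one assessment of off-treatment eGFR in Part 2".

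**Other sets for comparison.** Protocol 8.3 defines the Long-term Full Analysis Set as "all participants in the Long-term Safety Set who have at least 1 on-treatment measurement of eGFR in Part 2", and the Long-term Efficacy Analysis Set is its subset randomized to lixivaptan. In Part 1 the SAP computes the same kind of slope (8.3.1) in the SEAS, whose members are those "who have both baseline and at least one on-treatment assessment of eGFR".

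**Method.** Protocol 8.7.1 specifies an MMRM. SAP 8.9.1 averages the observed changes at each visit and applies a linear contrast with divisor 14.

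**Change log.** SAP 15 records the new Part 2 sets, with a general statement that they are better suited to Part 2. It does not discuss the slope and does not list the loss of the MMRM.

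**The concern.** Entry to the P2EAS depends on a blood draw off drug, which for most people comes after treatment has ended. That suits the off-treatment comparisons in SAP 8.7 and 8.8. For the on-treatment slope it discards creatinine values already collected, up to 13 per person, for a reason unrelated to the endpoint. If those who leave without such a draw have a different slope, the reported slope describes the people who were retained and not everyone treated.

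The slope supports the reading that the effect persists into year 2. Nothing else in the plan would expose the selection. The Part 2 disposition table (SAP 7.1) counts the P2SS and the P2EAS but not participants with on-treatment eGFR. SAP 8.8 tests only the off-treatment comparison. The Part 1 slope has sensitivity analyses (SAP 8.3.1.1); the Part 2 slope has none.

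The raw visit means add a second route to the same problem: an early leaver counts in the early means and vanishes from the later ones.

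**Working it through.** **1. Set membership, side by side**

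| Set | Source | eGFR required |
|---|---|---|
| Long-term Full and Efficacy Analysis Sets | Protocol 8.3 | at least 1 on-treatment, Part 2 |
| SEAS (Part 1 slope) | SAP 5, 8.3.1 | baseline and at least 1 on-treatment |
| P2EAS (Part 2 slope) | SAP 5, 8.9.1 | at least 1 off-treatment, Part 2 |

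Only the last conditions an on-treatment slope on an off-treatment value.

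**2. The plan's own figures**

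- Contrast coefficients −6 to 6 times weeks 4, 8, …, 52 sum to 728, and 728/52 = 14, as SAP 8.3.1 states.
- 0.90 × 1350 = 1215 expected in Part 2. At 2:1, and assuming equal retention, 1215 × 2/3 = 810 are in the Lixivaptan/Lixivaptan cohort.
- The documents give no size for the Part 2 slope set.

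**3. Effect of the set rule**

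Assume that a share d leaves with no off-treatment eGFR and that their slope differs from the retained slope s by D.

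- All-participant slope = (1 − d)s + d(s + D) = s + dD.
- P2EAS slope = s.
- Size of the difference = d × |D|.

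| d (of 810) | \|D\| = 1 | \|D\| = 2 | \|D\| = 4 |
|---|---|---|---|
| 2% (about 16) | 0.02 | 0.04 | 0.08 |
| 5% (about 40) | 0.05 | 0.10 | 0.20 |
| 10% (81) | 0.10 | 0.20 | 0.40 |

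Units are mL/min/1.73 m² per year. Every d and D is assumed.

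**4. Would changing the set alone help?**

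Keep the SAP's raw visit means, but admit everyone with an on-treatment value. Assume s = −2.0 and last visits spread evenly over the 1st to 12th of the 13 visits, so a leaver has 6.5 values on average. A share f_k = d(13 − k)/12 of the cohort then consists of leavers still present at visit k (k = 1 to 13). With t_k = 4k/52 years, the visit mean is

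m_k = t_k × [(1 − d)s + f_k(s + D)] / [(1 − d) + f_k],

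and the slope is the sum of (k − 7)m_k, divided by 14.

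| d, D | All participants | P2EAS | On-treatment set, raw means |
|---|---|---|---|
| 5%, −3 | −2.15 | −2.00 | −1.988 |
| 10%, −4 | −2.40 | −2.00 | −1.97 |

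Take the first row. At the first visit all leavers are present and the mean is −2.15 × 4/52 = −0.165, against −2.00 × 4/52 = −0.154 without them. At the last visit no leaver remains and the mean is −2.00 either way. Lowering only the early means flattens the line. If leavers instead all complete Visit 42 and then miss follow-up, the raw-mean contrast in the on-treatment set recovers −2.15. The set change is therefore needed, but it suffices only in that special case.

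**The case against.** **Few people may be excluded.** A reader might infer that anyone who skips Visits 43 to 45 is lost. The documents do not support that. The P2EAS needs any one off-treatment eGFR in Part 2, with no 8-day condition. Visit 42/ET draws creatinine up to 7 days after the last dose (Protocol 6.7.2), interruptions expected to last 7 days or more trigger draws (Protocol 4.2.3), and early stoppers are sent into Follow-up Period II (Protocol 4.2.4). This limits the number but does not justify the rule.

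**The Part 1 comparator.** A reader might infer that the Part 2 slope is set beside the SEAS slope, so that the comparison is tilted by design. SAP 8.9.1 shows Part 1 results for the participants of each treatment cohort, and SAP 6.1.2 defines the cohorts among those in Part 2. What remains is an ambiguity: the text does not say whether the P2EAS filter and the same estimator apply to the Part 1 column.

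**Under the SAP's estimator the set hardly matters.** In the 5% example it moves the slope from −2.000 to −1.988, and away from the all-participant value. This is correct, and it is why the estimator must change with the set.

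**Low stakes.** The slope is descriptive, open-label and outside the testing hierarchy. Protocol 8.7.1 names no analysis set, and Protocol 8.14 lets the SAP modify plans. So there is no type I error issue and no breach of the protocol.

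**Conclusion.** The mismatch stands as a minor flaw in the plan. SAP 8.9.1 with SAP 5 conditions an on-treatment slope on an off-treatment value, contrary to the protocol's Part 2 sets and the SAP's own Part 1 practice, and an unlisted change of estimator adds to the selection on retention.

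On assumed values the set rule shifts the slope by d × |D|, or 0.02 to 0.40 mL/min/1.73 m² per year for d from 2% to 10% and |D| from 1 to 4. A reader might infer that the slope is biased toward persistence of effect. That requires leavers to decline faster, which is plausible but stated nowhere; with D of the opposite sign the shift reverses.

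SAP 12 reports that the study ended early with 5 randomized and that no statistical analyses will be run, so no reported result is affected.

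**What to change.** - **SAP 5:** add a Part 2 on-treatment set as in Protocol 8.3, requiring at least 1 dose of lixivaptan and at least 1 on-treatment eGFR in Part 2.
- **SAP 8.9.1:** name that set and estimate the slope with the Protocol 8.7.1 MMRM, fitted by treatment cohort, in place of raw visit means. The existing contrast can be applied to the model's visit estimates. State which visits enter, since the protocol counts from Visit 29 and the SAP from Visit 30. The MMRM uses partial records under a missing-at-random assumption; it does not protect against departures from that.
- **SAP 8.9.1, Part 1 column:** state that it uses the same participants and the same model.
- **SAP 8.7 and 8.8:** keep the P2EAS.
- **SAP 15:** if raw visit means are retained, list the change and give the reason.

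The cost is SAP wording, one population flag and a model that the protocol already specifies. No new data are needed.

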2.2.4. Secondary Safety Objective

To assess the non-hepatic safety and tolerability of lixivaptan.

2.2.5. Health Outcomes Related Objectives

- To evaluate medical resource utilization (e.g., medication use/changes; unplanned office visits; urgent care and emergency department usage; and hospitalizations) resulting from clinical events in participants on lixivaptan;
- To evaluate the change in domain scores of the ADPKD-IS, ADPKD-PDS, and ADPKD-UIS.

2.2.6. Pharmacokinetics Objective

To further characterize the PK profile of lixivaptan utilizing PopPK based on sparse plasma sampling.

2.2.7. Exploratory Objectives

- To assess the effect of lixivaptan on htLV as measured by MRI following 52 weeks of open-label treatment;
- To evaluate the change in urine osmolality;
- To evaluate the effect of lixivaptan on kidney function as assessed by eGFR using the CKD-EPIcr-cys R equation following 52 weeks of open-label treatment.

3. Study Design

3.1. Overall Design

Figure 1: Part 1 Study Schematic

_	3 to 8 weeks	1 week	5 to 6 weeks	52 week	Up to 4 weeks	
	Screening Period	SB PBO Run-in	Lixivaptan Titration	Double-blind Randomized Treatment Period	Lixivaptan	Follow-up Period I
		Period	Period	Double-blind Randomized Treatment Period	- Matching Placebo	
v	la Vlb V	2 V 3	8 V4V9	V10	V2	2 V23V25

SB = Single-Blind, PBO = Placebo

Figure 2: Part 2 Study Schematic

3.2. Study Population

A total of 1350 participants with ADPKD who meet all inclusion criteria and none of the exclusion criteria (see below) and tolerate the study medications are planned to be randomized in the study at approximately 250 sites globally.

3.2.1. Inclusion Criteria

The following are requirements for entry into the study:

- 1. Male or female, between 18 and 60 years of age (inclusive) at the time of Screening (Visit 1a).
- 2. Diagnosis of ADPKD by modified Pei criteria:
 - For participants with family history of ADPKD, by ultrasound:
 - 18-39 years: \geq 3 cysts, unilateral or bilateral;
 - 40-59 years: ≥ 2 cysts in each kidney;
 - \circ 60 years: \geq 4 cysts in each kidney; or
 - For participants with family history of ADPKD, by computerized tomography (CT) or MRI:
 - 18-40 years: \geq 10 cysts in both kidneys; or
 - For participants without family history of ADPKD
 - a minimum of 10 cysts per kidney by any radiologic method and exclusion of other cystic kidney diseases (multiple simple kidney cysts, renal tubular acidosis, cystic dysplasia of the kidney, multicystic kidney, multilocular cysts of the kidney, medullary cystic kidney and acquired cystic disease of the kidney); or
 - genetic diagnosis of ADPKD.
- 3. At risk for rapid progression of ADPKD as based on the Mayo Clinic ADPKD Image Classification of 1C, 1D, or 1E based on age and height-adjusted TKV as determined by kidney MRI obtained during Screening, where class (class 1 [typical] versus class 2 [atypical]) and TKV are determined by a central imaging vendor.

- 4. eGFR ≥25 mL/min/1.73 m2 and ≤90 mL/min/1.73 m² based on the mean of 2 eGFR determinations (Visits 1a and 2 or Visits 1b and 2, if Visit 1b is required) calculated by the 2021 Chronic Kidney Disease Epidemiology Collaboration (CKD-EPI) eGFR creatinine equation refit without the race variable (CKD-EPIcr_R) from serum creatinine values obtained during Screening.
- 5. Appropriate control of hypertension for a minimum of 3 weeks including the use of an angiotensin converting enzyme inhibitor or angiotensin receptor blocker (unless not considered appropriate for the participant) as suggested by the 2021 Kidney Disease Improving Global Outcomes (KDIGO) "Clinical Practice Guideline for the Management of Blood Pressure in Chronic Kidney Disease," without the use of a diuretic.
- 6. Body mass index (BMI) between 18 and 40 kg/m² (inclusive) at the time of Screening.
- 7. Female participants must:

a. not be pregnant, lactating, or breastfeeding.

b. be either postmenopausal (defined as amenorrhea for ≥ 12 months), surgically sterile (defined as having undergone hysterectomy and/or bilateral oophorectomy) or, if of child-bearing potential, agree to practice acceptable methods of birth control or remain abstinent (only if this is the usual and preferred lifestyle of the participant) during the full duration of the trial and for 30 days after the last dose of study drug. Birth control methods that can be used during the study include the following:

- hormonal contraceptives: combined (estrogen and progestogen containing) hormonal contraception associated with inhibition of ovulation (i.e., oral, intravaginal, transdermal); progestogen-only hormonal contraception (i.e., oral, injectable, implantable). Note: in women with severe polycystic liver disease, contraceptives containing estrogen (and hormone replacement therapy) may be involved in the development and growth of liver cysts and polycystic liver disease progression; the supplemental risk of initiating or continuing estrogen treatment, as well as potential alternative contraceptives for WOCBP will be discussed with the potential participant
- intrauterine device (IUD), including progestin-containing intrauterine devices
- intrauterine hormone-releasing system (IUS)
- male sexual partner who has been vasectomized for at least 3 months prior to Screening and who has obtained a follow-up negative sperm count and is the sole sexual partner
- bilateral tubal ligation
- Essure® procedure (tubal occlusion)
- male or female condom with spermicide (cream, spray, gel, suppository, or polymer film)

- diaphragm, cervical cap, or contraceptive sponge with spermicide (with or without male condom).
- 8. Male participants must agree to use an acceptable form of birth control or remain abstinent (only if this is the usual and preferred lifestyle of the participant) during the full duration of the trial and for 30 days after the last dose of study drug.
- 9. Have read, understood, and provided written informed consent after the nature of the study has been fully explained and must be willing to comply with protocol requirements and study-related procedures.

